6.2.3. Definition of Baseline and Postbaseline Measures

The baseline value for efficacy and health outcomes variables measured at scheduled visits is defined as the last nonmissing measurement on or prior to the date of first study drug administration (expected at Week 0, Visit 2).

The baseline value for the daily diary assessments (Itch NRS, ADSS, Skin Pain NRS, PGI-S-AD) is defined as the mean of the nonmissing assessments in the 7 days prior to the date of first study drug administration.

If there are less than 4 nonmissing assessments in the baseline diary window, the interval lower bound can be extended up to 7 additional days, 1 day at a time, to obtain the 4 most recent nonmissing values. If there are not at least 4 nonmissing assessments in the baseline period, the baseline mean is missing.

Baseline for the safety analyses is defined as the last nonmissing scheduled (planned) measurement on or prior to the date of first study drug administration for continuous measures

by-visit analyses and all nonmissing measurements on or prior to the date of first study drug administration for all other analyses.

Postbaseline

Postbaseline measurements are collected after study drug administration for electronic patient-reported outcome (ePRO), Itch NRS, Skin Pain NRS, ADSS and PGI-S-AD up to Week 16 (Visit 8). Other postbaseline measurements are collected up to Week 104 (Visit 15).

Postbaseline for the safety analyses is defined as the nonmissing scheduled (planned) measurements after the date of first study drug administration for continuous measures by visit analyses and all nonmissing measurements after the date of first study drug administration for all other analyses.

Nonmissing efficacy data collected at scheduled visits (e.g., = Electronic version of Clinical Outcome Assessment [eCOA], clinician-reported outcome [ClinRO]) will be used for analyses. If an assessment is missing at a scheduled visit, an unscheduled postbaseline assessment can be used provided it falls within a ± 4 day window of the scheduled visit date. If there is more than 1 unscheduled visit within the defined visit window and no scheduled visit assessment is available, the unscheduled visit closest to the scheduled visit date will be used. If 2 unscheduled visits of equal distance are available, then the latter of the 2 will be used. If there is no nonmissing measure collected at the scheduled visit, or an unscheduled visit falling within the visit window, the assessment is missing for that scheduled visit.

For Treatment Period 1, postbaseline daily diary endpoints will be the mean of weekly visit windows (diary windows) anchored on day of first dose (Day 1) for Week 1 to Week 14 as follows:

Week	1	2	3	4	5	6	7	8	9	10	11	12	13	14
Day	1-7	8-14	21	22-28	29-35	36-42	43-49	50-56	57-63	64-70	71-77	78-84	85-91	92-98

Week 16 Daily Diary Window Construction

The following sequential steps will be used to determine the Week 16 diary window. The general goal is to anchor on the scheduled Week 16 visit (or a proximal unscheduled visit) if such a visit exists, or to use an interval based on days in study for cases where a scheduled Week 16 or a proximal surrogate does not exist.

Step 1: If the Week 16 scheduled visit exists, the Week 16 diary interval is the 7 days prior to the Week 16 date provided that window has at least 4 nonmissing observations. If there are less than 4 nonmissing observations, the diary window's lower bound will be extended 1 day at a time (up to day 99) to a maximum of 14 days prior to the Week 16 date until 4 nonmissing observations are obtained. If, after extending this diary window's lower bound to 14 days, there are less than 4 nonmissing observations then go to Step 3.

Step 2: If the Week 16 scheduled visit does not exist, the 7 days prior to the last visit (scheduled or unscheduled) occurring after Day 105 and up to Visit 8 will constitute the Week 16 diary

window provided that window contains at least 4 nonmissing observations. If there are less than 4 nonmissing observations, the diary window's lower bound will be extended 1 day at a time (up to Day 99) to a maximum of 14 days prior to the unscheduled visit date until 4 nonmissing observations are obtained. If, after extending this diary window's lower bound to 14 days, there are less than 4 nonmissing observations then go to Step 3.

Step 3: If neither a Week 16 scheduled visit is available or an unscheduled visit to act as a surrogate for the Week 16 diary window, then the Week 16 window will be Day 106 to Day 112. If there are less than 4 nonmissing observations, the dairy window's lower bound will be extended 1 day at a time to Day 99 until 4 nonmissing observations are obtained.

If the steps above do not detect a window with at least 4 nonmissing observations then the Week 16 window is 7 days from either the Week 16 visit, the surrogate visit or Day 106 to Day 112 and the mean is missing and subject to imputation rules.

Week 15 Daily Diary Window Construction

The lower boundary of the Week 15 diary window is defined as Day 99. The upper bound of the Week 15 diary window is the minimum of either Day 105 or the lower bound of the Week 16 diary window -1. Consequently, Week 15 may be less than 4 days if the Week 16 scheduled visit is before Day 112. Moreover, as Week 15 diary window cannot exceed 7 days, there could be daily assessments between Week 15 and Week 16 diary windows that do not fall into a diary window. If after constructing the diary windows, there are fewer than 4 nonmissing values the mean for Week 15 is missing and subject to imputation rules.

Handling of Duplicate Diary Records

If there is more than 1 diary record on a particular date, the first record on that particular date will be used in the analysis.

Postbaseline measures for the safety analyses are defined as the nonmissing scheduled (planned) measurements after the date of first study drug administration for continuous measures by-visit analyses and all nonmissing measurements after the date of first study drug administration for all other analyses.

6.2.4. Analysis Methods

Unless otherwise specified, all analyses described in this section will compare estimates (eg, odds ratios, least square means, proportions) of baricitinib 1-mg and 2-mg to placebo. Thus odds ratios are baricitinib treatment groups relative to placebo; similarly, least-square mean (LSM) differences and differences in proportions are between baricitinib treatment groups and placebo.

The main analysis method of categorical efficacy variables and health outcomes variables will use a logistic regression analysis with baseline disease severity (IGA), baseline value, and treatment group in the model. Firth's correction will be used in order to accommodate (potential) sparse response rates. The p-value for the odds ratio from the logistic regression model will be used for statistical inference, unless Firth's correction still results in quasi-separation. In that case, Fisher's exact test will be used for statistical inference. The difference

in percentages and $100(1-\alpha)\%$ CI of the difference in percentages using the Newcombe-Wilson method without continuity correction will be reported. The p-value from the Fisher's exact test will also be produced as a secondary analysis.

The main analysis method for all continuous efficacy and health outcomes variables will use mixed model repeated measures (MMRM) analysis. The MMRM model will use a restricted maximum likelihood (REML) estimation. The model will include treatment, baseline disease severity (IGA), visit, and treatment-by-visit-interaction as fixed categorical effects and baseline and baseline-by-visit-interaction as fixed continuous effects. For daily diary assessments, the model for analyses up to Week 16 will include all weekly assessments. An unstructured (co)variance structure will be used to model the between- and within-patient errors. If this analysis fails to converge, the heterogeneous autoregressive [ARH(1)], followed by the heterogeneous compound symmetry (CSH), followed by the heterogeneous Toeplitz (TOEPH), followed by autoregressive[AR(1)], followed by compound symmetry (CS) will be used. The Kenward-Roger method will be used to estimate the degrees of freedom. Treatment LSMs will be estimated within the framework of the MMRM using type 3 sums of squares. Differences in LSM between each dose of baricitinib and placebo (and associated p-values, standard errors and $100(1-\alpha)\%$ CI) will be used for statistical inference. The LSM difference, standard error, p-value and $100(1-\alpha)\%$ CI will be reported.

Treatment comparisons for continuous efficacy and health outcomes variables may also be made using analysis of covariance (ANCOVA) for key secondary and secondary objectives. When an ANCOVA model is used, the model includes baseline disease severity (IGA), treatment group, and baseline value. Treatment LSMs will be estimated within the framework of the ANCOVA using type 3 sums of squares. Reported differences in LSM and associated p-values, standard errors, and $100(1-\alpha)\%$ CI will be used for statistical inference.

Fisher's exact test will be used to test the difference between each baricitinib dose and placebo in proportion of patients experiencing adverse events (AEs), discontinuation from study drug, and other categorical safety data. Continuous vital signs, body weight, and other continuous safety variables, including laboratory variables, will be analyzed by an ANCOVA with treatment group and baseline value in the model. The significance of within-treatment group changes from baseline will be evaluated by testing whether or not the treatment group LSM changes from baseline are different from zero; the standard error for the LSM change will also be displayed. Differences in LSM will be displayed, with the p-value associated with the LSM comparison to placebo and a 95% CI on the LSM difference also provided. In addition to the LSMs for each group, the within-group p-value for the change from baseline will be displayed.

Time to event will be analyzed using cumulative incidence function with observed values, defining first time reaching the event IGA (0,1), EASI 75, or Itch NRS 4-pt improvement before rescue as onset, treating rescue and discontinuing for lack of efficacy as competing event censor up to Week 16.

For final database lock, the main analysis method for efficacy and health outcomes variables will use descriptive summary per observed and mLOCF data.

6.2.5. Derived Data

The following endpoints are derived from collected data:

- Age (year), derived using first dose date as the reference start date and July 1 of birth year, and truncated to a whole-year (integer) age. Patients whose derived age is less than 18 will have the required minimum age of 18 at informed consent confirmed. Reporting for age, age groups, and lab ranges, however, will be based on their derived age.
- Age group (<65, \geq 65 years old)
- Age group (<65, \geq 65 to <75, \geq 75 to <85, \geq 85 years old)
- Body mass index (BMI) (kg/m²) = Weight (kg)/((Height (cm)/100)²)
- BMI category (<25 kg/m², \geq 25 to <30 kg/m², \geq 30 kg/m²)
- The duration of AD from diagnosis (year) = [(Date of informed consent – Date of AD diagnosis)+1]/ 365.25.

If year of onset is missing, duration of AD will be set as missing. Otherwise, unknown month will be taken as January, and unknown day will be taken as 01. The duration of AD will be rounded to 1 decimal place.

- Duration of AD (years) category (0 to <2 years, \geq 2 to <5 years, \geq 5 to <10 years, \geq 10 to <20 years, \geq 20 years)
- Diagnosis age: (number of months between date of AD diagnosis and July 1 of birth year) / 12, and truncated to a whole-integer age
- Diagnosis age group (<18, \geq 18 and <50, \geq 50 years old)
- Change from baseline = postbaseline measurement at Visit x – baseline measurement. If a baseline value is missing, it will not be imputed and the change from baseline will not be calculated.
- Percent change from baseline at Visit x:

((Postbaseline measurement at Visit x - Baseline measurement)/Baseline measurement)*100.

If a baseline value is missing, it will not be imputed and percent change from baseline will not be calculated.

- Weight (kg) = weight (lbs) * 0.454.
- Weight category (<60 kg, \geq 60 to <100 kg, \geq 100 kg)
- Height (cm) = height (in) * 2.54.
- Cyclosporine inadequate efficacy response(yes, no)
 - Set yes if the reason for discontinuation is inadequate response
- Cyclosporine intolerance (yes, no)
 - Set yes if the reasons for discontinuation are: intolerance to medication or contraindication (physician indicated cyclosporine was used and a contraindication was noted)
- Cyclosporine contraindication [ineligible] (yes, no)
 - Set to yes if cyclosporine never used because of a contraindication
- Cyclosporine inadvisable (yes, no)

- Set to **yes** if the following reasons were selected for either not using the medication or discontinuing the medication:
 - Reason for not using medication: contraindication, unfavorable benefit/risk, or physician decision
 - Reason for discontinuation: inadequate response, intolerance to medication, or contraindication.
- topical calcineurin inhibitor inadequate efficacy response (yes, no)
 - Set **yes** if the reason for discontinuation is inadequate response
- topical calcineurin inhibitor intolerance (yes, no)
 - Set **yes** if the reasons for discontinuation are: intolerance to medication or contraindication (Physician indicated TCNI was used and a contraindication was noted)
- topical calcineurin inhibitor contraindication / [ineligible](yes, no)
 - Set to **yes** if TCNI never used because of a contraindication
- topical calcineurin inhibitor inadvisable (yes, no)
 - Set to **yes** if the following reasons were selected for either not using the medication or discontinuing the medication:
 - Reason for not using medication: Physician decision, concern about side effects, unfavorable benefit risk, contraindication
 - Reasons for discontinuation: inadequate response, intolerance to medication, or contraindication

6.3. Adjustments for Covariates

The randomization to treatment groups at Week 0 (Visit 2) is stratified by disease severity (IGA) as described in Section 5.1. Unless otherwise specified, the statistical analysis models will control for disease severity. The covariates used in the logistic model for categorical data will include the parameter value at baseline. The covariates used in the ANCOVA models for continuous data generally will include the parameter's value at baseline. Inclusion of baseline in the ANCOVA models ensures treatment LSMS are estimated at the same baseline value. When an MMRM analysis is performed, baseline value and baseline-by-visit interactions will be included as covariates.

6.4. Handling of Dropouts or Missing Data

Intercurrent events (International Conference on Harmonisation [ICH] E9 R1) are events which occur after the treatment initiation and make it impossible to measure a variable or influence how it would be interpreted.

Depending on the estimand being addressed, different methods will be used to handle missing data as a result of intercurrent events. Intercurrent events can occur through the following:

- application of one of the censoring rules (including after permanent study drug discontinuation, after rescue therapy)
- discontinuation from the study

- missing an intermediate visit prior to discontinuation or rescue, and
- lost to follow-up.

Non-censor intercurrent events are events that are not due to the application of any censoring rule (ie, the last 3 items in the list above).

Note that as efficacy and health outcome data can accrue after a patient permanently discontinues study drug or begins rescue therapy, specific general censoring rules to the data will be applied to all efficacy and health outcome observations subsequent to these events depending on the estimand being addressed. These specific censoring rules applied to Week 16 interim analyses are described below.

The *primary censoring rule* will censor efficacy and health outcome data after permanent study drug discontinuation or after rescue therapy. This censoring rule will be applied to all continuous and categorical efficacy and health outcome endpoints. Alternatively, this censoring rule is equivalent to using all the data up to rescue.

A *secondary censoring rule* will only censor efficacy and health outcome data after permanent study drug discontinuation. As patients who are rescued to systemic therapies are required to permanently discontinue study drug, they will also have post-rescue observations censored. The secondary censoring rule will be applied to primary and key secondary efficacy and health outcome endpoints.

After Week 16, concomitant use of low-potency TCS is allowed. Data collected after permanent study drug discontinuation is excluded. This rule will be applied to the final DBL.

Non-responder imputation (for categorical variables) and MMRM (for continuous variables) will be the primary methods used to handle missing data. Censoring rules, along with their associated estimator assumptions, are described in Sections 6.4.1 through 6.4.6.

Table JAIW.6.1 summarizes how imputation techniques and censoring rules are applied to efficacy and health outcome endpoints.

Table JAIW.6.1. Imputation Techniques for Various Variables

Efficacy and Health Outcome Endpoints	Imputation Method
IGA(0,1), EASI75, 4-point Itch NRS improvement	NRI ^{ab} , pMI ^a , Tipping point ^a , mLOCF
EASI90, SCORAD75	NRI ^{ab} , pMI ^a
EASI percent change, ADSS Item 2 change, Skin Pain NRS change	MMRM ^{ab} , mLOCF ^a , pMI ^a , mBOCF ^a
All remaining categorical measures	NRI ^a , mLOCF
All remaining continuous efficacy and health outcome measures in secondary analysis	MMRM ^a , mLOCF ^a
All continuous efficacy and health outcome measures in exploratory analysis	MMRM ^a

Abbreviations: AD = atopic dermatitis; ADSS = Atopic Dermatitis Sleep Scale; EASI = Eczema Area and Severity Index score; IGA = Investigator's Global Assessment for AD; mBOCF = baseline observation carried forward; mLOCF = modified last observation carried forward; MMRM = mixed model repeated measures; NRI = nonresponder imputation, NRS = Numeric Rating Scale; pMI = placebo multiple imputation; SCORAD = SCORing Atopic Dermatitis.

- a Analyses utilizing the primary censoring rule.
- b Analyses utilizing the secondary censoring rule.

Tipping Point, pMI, NRI, and MMRM (etc.) were used in the Week 16 interim DBL. The Final DBL only use observed and mLOCF.

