4.1. Primary Objective

The primary objective of this study is to test the hypothesis that baricitinib 2-mg once daily (QD) is superior to placebo in the treatment of patients with moderate to severe atopic dermatitis (AD), as assessed by the proportion of patients achieving EASI75 at Week 16.

The associated estimand for this objective is to measure the effect of baricitinib therapy as assessed by the proportion of patients achieving EASI75 at Week 16 assuming the treatment response disappears after patients are rescued or discontinue from study or treatment. See also Sections 6.4 and 6.4.1 on how this estimand handles outcomes after occurrence of any intercurrent event through non-responder imputation (NRI).

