Analysis: For continuous endpoints, fit its treatment response model (MMRM) for each completed data set. For the primary and secondary key efficacy endpoints of EASI75, IGA(0,1), EASI90, SCORAD75, and 4-point improvement from baseline in Itch NRS, the binary outcomes will be derived from the imputed data for each patient before fitting into the analysis model. A logistic regression model will be applied. For continuous endpoints, fit its treatment response model (MMRM) for each completed data set. For the primary and secondary key efficacy endpoints of EASI75, IGA(0,1), EASI90, SCORAD75, and 4-point improvement from baseline in Itch NRS, the binary outcomes will be derived from the imputed data for each patient before fitting into the analysis model. A logistic regression model will be applied.

The number of imputed data sets will be $m=100$ and a 6-digit seed value will be pre-specified for each analysis. Within the program, the seed will be used to generate the m seeds needed for imputation. The initial seed values are given in [Table JAIW.6.2](#).

Table JAIW.6.2. Seed Values for Multiple Imputation

Analysis	Seed Value
Proportion of patients achieving IGA of 0 or 1 with a ≥ 2 -point improvement from baseline at Week 16, using the primary censoring rule	123450
Percent change from baseline in EASI score at 16 weeks using the primary censoring rule. EASI75 and EASI90 will leverage imputation from EASI and therefore do not need a new seed number.	123451
Proportion of patients achieving SCORAD75 at 16 weeks using the primary censoring rule, with data up to rescue	123452
Proportions of patients achieving a 4-point improvement from baseline in Itch NRS at Week 16, using the primary censoring rule	123453
Mean change from baseline in Skin Pain NRS at Week 16 using the primary censoring rule	123454
Mean change from baseline in the score of Item 2 of the ADSS at Week 16 using the primary censoring rule	123455

Abbreviations: AD = atopic dermatitis; ADSS = Atopic Dermatitis Sleep Scale; EASI = Eczema Area and Severity Index score; IGA = Investigator's Global Assessment for AD; NRS = Numeric Rating Scale; SCORAD = SCORing Atopic Dermatitis.

The final inference on treatment difference is conducted from the multiple datasets using Rubin's combining rules, as implemented in SAS® PROC MIANALYZE.

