6.15. Subgroup Analyses

Subgroup analyses comparing each dose of baricitinib to placebo will be performed on the ITT population at Week 16, with data up to rescue for the following:

- proportion of patients achieving IGA 0 or 1
- proportion of patients achieving EASI75 Response Rate
- proportion of patients achieving Itch NRS 4-point improvement

The following subgroups, categorized into disease-related characteristics and demographic characteristics, will be evaluated:

- Patient Demographic and Characteristics Subgroups:
 - Gender (male, female)
 - Age Group (<65, \geq 65 years old)
 - Age Group (<65, \geq 65 to <75, \geq 75 to <85, \geq 85 years old)
 - Baseline Weight (<60 kg, \geq 60 to <100 kg, \geq 100 kg)
 - Baseline BMI (<25 kg/m², \geq 25 to <30 kg/m², \geq 30 kg/m²)
 - Race (American Indian or Alaska Native, Asian, Black or African American, Native Hawaiian or Other Pacific Islander, White, Multiple)
 - Baseline Renal Function Status: impaired (eGFR <60 mL/min/1.73 m²) or not impaired (eGFR \geq 60 mL/min/1.73 m²)
 - Prior systemic therapy use (yes, no)
- Baseline Disease-Related Characteristics Subgroup
 - Baseline Disease Severity (IGA score): 3, 4

Descriptive statistics will be provided for each treatment and stratum of a subgroup as outlined, regardless of sample size. The subgroup analyses for categorical outcomes will be performed using logistic regression using Firth's correction to accommodate (potential) sparse response rates.. The model will include the categorical outcome as the dependent variable and baseline

value (for EASI and itch), baseline severity, treatment, subgroup, and treatment-by-subgroup interaction as explanatory variables. Missing data will be imputed using NRI (Section 6.4.1). The treatment-by-subgroup interaction comparing treatment groups will be tested at the 0.1 significance level. The p-value from the logistic regression model will be reported for the interaction test and the subgroup test, unless the model did not converge. Response counts and percentages will be summarized by treatment for each subgroup category. The difference in percentages and 100(1-alpha)% CI of the difference in percentages using the Newcombe-Wilson without continuity correction will be reported. The p-value from the Fisher's exact test will also be produced.

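### Section 6.4 wrongly equates the primary censoring rule with using all data up to rescue; the one place this wording serves as the data rule is the subgroup section, 6.15

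*SAP*

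**What the plan says.** SAP Section 6.4 states that the primary censoring rule "will censor efficacy and health outcome data after permanent study drug discontinuation or after rescue therapy". After one sentence on which endpoints it covers, the section adds, as an alternative statement, that "this censoring rule is equivalent to using all the data up to rescue". Earlier in the same section the SAP notes that "efficacy and health outcome data can accrue after a patient permanently discontinues study drug or begins rescue therapy". On the link between the two events it says only that "patients who are rescued to systemic therapies are required to permanently discontinue study drug". It nowhere says that stopping study drug counts as rescue.

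The primary estimand in Section 4.1 is framed "assuming the treatment response disappears after patients are rescued or discontinue from study or treatment", and Section 6.11.1 repeats this. Section 6.4.1 applies NRI, under the primary rule, to patients who were rescued or who permanently stopped study drug. Step 4 of the imputation procedure in Section 6.4.5 also keeps observed values only up to drug discontinuation and/or rescue.

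The up-to-rescue wording returns in two places. Section 6.15 says that the subgroup analyses "will be performed on the ITT population at Week 16, with data up to rescue for the following" three binary endpoints, one of which is EASI75. A seed entry in Table JAIW.6.2 reads "Proportion of patients achieving SCORAD75 at 16 weeks using the primary censoring rule, with data up to rescue".

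**The concern.** The definition has two triggers and the restatement has one. They select the same data only if no unrescued patient contributes an assessment after stopping study drug, and Section 6.4 itself allows for such data. For those patients the two wordings give different Week 16 outcomes: non-response by rule, or whatever was observed.

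The restatement also disturbs the relation between the two censoring rules. The secondary rule censors only at permanent drug discontinuation, so the primary rule, as defined, is the secondary rule plus rescue. Read as up to rescue only, the primary rule would keep off-drug data that the secondary rule removes, and a comparison of the two would no longer isolate the handling of rescue.

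What is at stake is mainly Section 6.15. A programmer who takes its wording at face value could build an EASI75 data set whose overall responder counts do not reconcile with the primary analysis.

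**Working it through.** **1. The two wordings, by type of patient.** Assume an assessment exists at Week 16.

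| Patient before Week 16 | Definition (6.4) | Restatement (6.4) | Primary estimand (4.1, 6.11.1) |
|---|---|---|---|
| On drug, not rescued | kept | kept | observed response |
| Rescued, still on drug | censored, NRI | censored, NRI | response lost |
| Rescued to systemic therapy, drug stopped | censored, NRI | censored, NRI | response lost |
| Drug stopped, not rescued | censored, NRI | **kept** | response lost |

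Only the last row differs, and there the definition agrees with the estimand and the restatement does not. The link stated in 6.4 runs from systemic rescue to drug discontinuation. The converse, which would empty the last row, is not stated.

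**2. Which places depend on the restatement.**
- Sections 4.1, 6.4.1, 6.4.5 (step 4) and 6.11.1 each carry discontinuation as a trigger and do not depend on it.
- Table JAIW.6.2 names the primary censoring rule and adds the loose wording as a gloss. It is a seed label and defines no data set.
- Section 6.15 does not name the primary censoring rule. It gives the up-to-rescue wording as its data rule and sends missing data to Section 6.4.1, which uses both triggers. Taken literally, the two parts of 6.15 disagree for the last row of the table.

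**3. The plan's own figure.** The point changes no stated number, but the planning case in Section 6.1 gives a scale. The inputs are 10% and 20% response, two-sided alpha 0.05 (Section 6.1) and about 150 per arm (Section 5). With pooled variance under the null:

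- null SE = √(2 × 0.15 × 0.85 / 150) = 0.04123
- alternative SE = √((0.10 × 0.90 + 0.20 × 0.80) / 150) = 0.04082
- power = Φ((0.10 − 1.96 × 0.04123) / 0.04082) = Φ(0.470) = 68.1%

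This reproduces the stated figure of at least 68%.

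**4. Illustration under assumptions.** The SAP gives neither the share of patients who are off drug, unrescued and assessed at Week 16, nor their response rate. Assume a share of 2% to 10% per arm (3 to 15 of 150), of whom 10% to 30% meet EASI75. The restatement then counts 150 × 0.02 × 0.10 = 0.3 to 150 × 0.10 × 0.30 = 4.5 more responders per arm.

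- Equal in both arms: power moves from 68.1% to between 67.6% and 61.7%.
- In one arm only, at the extreme (10% share, 30% response): 37.1% if placebo only, 86.2% if 2-mg only.

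The direction depends entirely on the assumed imbalance. In terms of p-values from the pooled chi-squared test with 150 per arm:

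- 15 v 30 responders: p = 0.015
- three added to placebo only, 18 v 30: p = 0.059
- three added to each arm, 18 v 33: p = 0.021

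The placebo-only case is a one-arm extreme, and the planned test is Firth logistic regression (Section 6.2.4), not chi-squared.

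**The case against.** The strongest defence is that the sentence is loose shorthand and that the rest of the document controls. Both censoring rules stop at permanent drug discontinuation, and the primary rule differs only by also stopping at rescue. On that view the up-to-rescue wording merely picks the primary rule over the secondary one. Sections 6.4.1 and 6.4.5 use similar shorthand when they speak of censoring on rescue. Section 6.15 cites Section 6.4.1, which covers all categorical endpoints with both triggers, so the subgroup rule can be recovered. The Week 16 lock has been executed (Section 6.2.1), and the final lock has its own rule, which excludes data after permanent drug discontinuation.

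Most of this stands. It explains the likely origin of the wording and limits the consequence. It does not make the sentence true, and it leaves the reader of 6.15 to work out that a stated data rule is not meant literally.

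A reader might infer more: that the primary analysis kept off-drug data, that two data sets are in fact specified for the primary endpoint, or that significance would be lost. The document does not support these. Sections 4.1, 6.4.1 and 6.11.1 fix the primary analysis, nothing shows which data the subgroup programs used, and the loss of significance needs an unsupported shift in the placebo arm alone.

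**Conclusion.** The point holds as an error of wording in a rule that governs the primary endpoint. The equivalence is false on the SAP's own terms and conflicts with the primary estimand for one type of patient: drug stopped, not rescued, still assessed. The intended primary analysis is not in doubt. The practical exposure is the subgroup analysis in Section 6.15, with a minor label in Table JAIW.6.2.

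No effect size can be stated, because the number of such patients and their response rate are not in the document. The power and p-value ranges above show only that the result depends on assumed counts and on how they split between arms. The correction should be made, but the point gives no ground for doubting the primary result.

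**What to change.** - Section 6.4: delete the sentence that begins with Alternatively, or reword it so that data are used up to the earlier of rescue and permanent study drug discontinuation.
- Section 6.15 and Table JAIW.6.2: replace the up-to-rescue wording with a reference to the primary censoring rule.
- Because the Week 16 lock has been executed, confirm that the subgroup programs and the SCORAD75 placebo multiple imputation program applied both triggers. If either did not, rerun it and report the number of patients affected by arm.

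The cost is wording in three places and a short check of existing programs. No change to the design, the sample size or the primary analysis is needed.
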